At visit 16 (the end of up-dosing) under intensive monitoring, all subjects who achieve 300 mg/day AR101 during the up-dosing phase for at least 2 weeks will undergo a post up-dosing DBPCFC up to 2044 mg (cumulative) peanut protein or placebo (see Appendix 1) to assess desensitization. At visit 22 (the end of maintenance period), all subjects who maintain 300 mg/day AR101 will undergo a post maintenance DBPCFC up to 2044 mg (cumulative) peanut protein or placebo to assess desensitization. Dosing with AR101 should continue on the days between the 2 parts of the DBPCFC. The subject's sensitivity to peanut allergen is defined as the dose at which the subject experiences allergic reactions. All symptoms and signs will be evaluated and rated based on a standardized oral food challenge scoring system (CoFAR) (see Appendix 2). Up-dosing during the DBPCFC will be stopped when the blinded assessor finds symptoms and/or signs that indicate a definite objective (Grade 1 [mild]) allergic reaction (CoFAR grading system [see Appendix 2]) has occurred based on clinically significant changes in reported symptoms, physical findings, or vital signs that the subject is experiencing to the challenge material. Vital signs will be assessed every 15 to 30 minutes. In addition, subjects will be considered to have dose-limiting reactions if they experience any mild subjective reactions requiring pharmacologic intervention and/or any moderate/severe reaction. The DBPCFC will consist of 8 doses (peanut protein or placebo), given every 15 to 30 minutes: 1, 3, 10, 30, 100, 300, 600, 1000 mg resulting in a total challenge of up to 2044 mg (cumulative) peanut protein. Both peanut and oat protein will be concealed in a food that masks the taste. The food challenges will be performed on different days (1-day placebo [oat] protein, 1-day peanut protein, with order determined at random) at least 24 hours, but not more than 7 days, apart, and not within 24 hours of a dose of study drug. Subjects will be considered to have passed the DBPCFC if they do not experience any objective Grade 1 (mild) reaction by CoFAR grading system (see Appendix 2). If the subject experiences reactions, he/she will be treated with the necessary rescue medications. In addition, subjects will be considered to have passed the DBPCFC if they do not experience any mild subjective symptoms requiring pharmacological intervention and/or moderate or severe symptoms. He/she will be observed for a minimum of 2 hours after the final administered dose and discharged only when deemed clinically stable by a study physician. Symptom severity will be adjudicated by an independent, blinded assessor who is not involved in subject study visit conduct. When dosing elicits an acute reaction characterized by the appearance of only a mild subjective symptom or symptoms, the investigator will be required to assess whether the dose was or was not tolerated. The determination of tolerability must be made on the basis of clinical judgement. The following are presented as guidelines for determining whether a dose associated with the emergence of a mild subjective

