9.2.2. Efficacy Procedures

9.2.2.1. Double-Blind Placebo-Controlled Food Challenge

The subject's sensitivity to peanut allergen is defined as the dose at which the subject experiences allergic reactions. All symptoms and signs will be evaluated and rated based on a standardized oral food challenge scoring system (see Appendix 2). Up-dosing during the DBPCFC will be stopped when the principal investigator (or designee) finds symptoms and/or signs that indicate a definite objective allergic reaction (CoFAR grading system [see Appendix 2]) has occurred based on clinically significant changes in reported symptoms, physical findings, or vital signs that the subject is experiencing to the challenge material. The challenge will consist of 8 doses (peanut protein or placebo), given every 15 to 30 minutes: 1, 3, 10, 30, 100, 300, 600, 1000 mg, up to 2044 mg peanut protein (cumulative). Both peanut and oat protein will be concealed in a food that masks the taste. The food challenges will be performed on different days (1-day placebo [oat] protein, 1-day peanut protein, with order determined at random) at least 24 hours, but not more than 7 days apart, and not within 24 hours of a dose of study drug. After the last dose of the DBPCFC, the subject will be monitored for at least 2 hours and then discharged from the clinic. Subjects will be considered to have tolerated the DBPCFC and passed if they do not experience any objective Grade 1 (mild) reaction by CoFAR grading system (see Appendix 2). If the subject experiences reactions, they will be treated with the necessary rescue medications. Symptom severity will be adjudicated by an independent, blinded assessor who is not involved in performing the baseline food challenge.

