3.2. The Per Protocol Set (PPS)

PPS includes all subjects in the mFAS except for those who are excluded because of important protocol violations. An important protocol violation is one that may affect the interpretation of study efficacy results. A preliminary list of such important protocol violations is provided in Section 10.6 and a final list of subjects excluded from FAS will be generated prior to primary analysis database lock. Final determinations of the PPS will be made in the blinded manner before data base lock.

The primary endpoint and first secondary endpoint will be evaluated on the PPS in addition to mFAS and FAS.

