4.5. Efficacy Variable

4.5.1. **Primary Efficacy Variable (s)**

The primary endpoint in this study is:

• Proportion of subjects treated with dupilumab plus AR101 vs placebo plus AR101 who "pass" a post up-dosing DBPCFC with 2044 mg (cumulative) peanut protein at visit 16

Double-blind placebo-controlled food challenge (DBPCFC)

At visit 16, under intensive monitoring, all subjects who achieve 300 mg/day AR101 during the up-dosing phase for at least 2 weeks will undergo a post up-dosing DBPCFC up to 2044 mg (cumulative) peanut protein or placebo to assess desensitization. At visit 22, all subjects who maintain 300 mg/day AR101 will undergo a post maintenance DBPCFC up to 2044 (cumulative) peanut protein or placebo to assess desensitization. The subject's sensitivity to peanut allergen is defined as the dose at which the subject experiences allergic reactions. All symptoms and signs will be evaluated and rated based on a standardized oral food challenge scoring system (CoFAR). Up-dosing during the DBPCFC will be stopped when the principal investigator (or designee) finds symptoms and/or signs that indicate a definite objective (Grade 1 [mild]) allergic reaction (CoFAR grading system) has occurred based on clinically significant changes in reported symptoms, physical findings, or vital signs that the subject is experiencing to the challenge material. Vital signs will be assessed every 15 to 30 minutes. In addition, subjects will be considered to have dose-limiting reactions if they experience any mild subjective reactions requiring pharmacologic intervention and/or any moderate/severe reaction.

The DBPCFC will consist of 8 doses (peanut protein or placebo), given every 15 to 30 minutes: 1, 3, 10, 30, 100, 300, 600, 1000 mg, up to 2044 mg peanut protein (cumulative). Both peanut and oat protein will be concealed in a food that masks the taste. The food challenge will be performed on different days (1-day placebo [oat] protein, 1-day peanut protein, with order determined at random) at least 24 hours, but not more than 7 days apart, and not within 24 hours of a dose of study drug. Subjects will be considered to have passed the DBPCFC if they do not experience any objective Grade 1 (mild) reaction by CoFAR grading system. If the subject experiences reactions,

Regeneron Pharmaceuticals, Inc. Statistical Analysis Plan

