- 5. The food challenges will be performed on different days (1-day placebo [oat] protein, 1-day peanut protein, with order determined at random) at least 24 hours, but not more than 7 days, apart and not within 24 hours of a dose of SC study drug. Subject will be observed for a minimum of 2 hours after the final administered dose and discharged only when deemed clinically stable by a study physician. On the day following a food challenge, the site must make a telephone contact to inquire if the subject experienced any AEs and report appropriately. Before each challenge, the subject will have a physical assessment performed by a trained physician's assistant, registered nurse, nurse practitioner, and/or physician of the study team who is blinded to the testing material. Eczema Area and Severity Index and ACQ only needed be completed once during day 1 of the food challenge.
- 6. Subjects should not take anti-histamines for at least 5 days prior to the SPT.
- 7. Site should confirm subject compliance at each clinic visit.
- 8. During DBPCFC, vital signs will be collected every 15 to 30 minutes.

Regeneron Pharmaceuticals, Inc. Statistical Analysis Plan

- 9. Spirometry will be performed in-clinic on the same day whenever FeNO measurement is scheduled; however, spirometry will also be performed at other visits when FeNO is not collected. FeNO should be done prior to spirometry. If the DBPCFC is scheduled on the day of the visit, then both FeNO measurement and spirometry will be performed twice before the subject goes home: once before DBPCFC, once after DBPCFC.
 - a. During the COVID-19 pandemic, measurements of FeNO no longer need to be completed while on study (although FeNO is still required at screening). Additionally, if spirometry cannot be completed after enrollment, peak flow may be performed instead at the discretion of the investigator (although spirometry is still required at screening).
- 10. Only for patients who discontinue for GI AEs. If applicable, after week 64 PEESS will be collected by phone.
- 11. On the day of the DBPCFCs, blood draws for optional exploratory research-will be performed before the DBPCFC is performed.
- 12. Clinic visits are monthly. However, SC study drug administration is Q2W and dosing diaries for AR101 and allergic symptoms are done daily.

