| Procedure not | Demographics were not collected at Screening V1 | |
| performed | | |
| Procedure not | Vital Signs were not collected at Screening V1, V1A, V16, V22, | |
| performed | V25 | |
| Procedure not | Physical Examination was not collected at Screening V1 | |
| performed | | |
| Procedure not | Pregnancy Test (serum) was not collected at Screening V1 for | |
| performed | WOCBP. | |
| Procedure not | Peanut sIgE was not collected at Screening V1 | |
| performed | | |
| Procedure not | Spirometry was not collected at Screening V1a | |
| performed | | |
| Procedure not | Randomization was not collected at Baseline V2 | |
| performed | | |
| Procedure not | 2 or more Blinded Study Drug SC Q2W Administration was not | 1 |
| performed | collected at Baseline V2, V3, V4, V5, V6, V7, V8, V9, V10, V11, | |
| * | V12, V13, V14, V15, V16, V17, V18, V19, V20 or V21 (up to | |
| | PA2) | |
| Procedure not | Pregnancy Test (urine) was not collected at Baseline V2, V3, V4, | |
| performed | V5, V6, V7, V8, V9, V10, V11, V12, V13, V14, V15, V16, V17, | |
| 1 | V18, V19, V20, V21, V22 or Early Termination Visit for wOCBP | |
| Procedure not | Pregnancy Test (serum) was not collected at V25 EOS for WOCBP | |
| performed | | |
| Procedure not | Randomization was not collected at V16 | |
| performed | | |
| Procedure not | DBPCFC was not collected at V16 | |
| performed | | |
| Procedure not | DBPCFC was not collected at V22 | |
| performed | | |
| Procedure not | 2 or more Blinded Study Drug SC Q2W Administration was not | |
| performed | collected at Baseline V2, V3, V4, V5, V6, V7, V8, V9, V10, V11, | |
| | V12, V13, V14, V15, V15a, V15b, V15c, V15d, V15e, V15f, V16, | |
| | V17, V18, V19, V20 or V21 or in USCHED (PA3 and after) | |
| Procedure not | Pregnancy Test (urine) was not collected at V15a, V15b, V15c, | |
| performed | V15d, V15e, V15f for WOCBP (PA3) | |
| Procedure not | Weight was not collected at Baseline V2 | |
| performed | č | |
| Procedure performed | Food challenges were not performed either on different day, more | 1 |
| outside of window | than 1 day apart or less than 7-days apart during DBPCFC at on- | |
| | study visit V16, V22 or V25 EOS | |
| Randomization Error | Stratification error | 1 |
| Randomization Error | Subject randomized twice | |
| Received an excluded | | |
| concomitant treatment | Subject received prohibited medication impacting safety or efficacy parameters and assessments treatment with a live (attenuated) | |

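### The preliminary deviation row for food-challenge spacing in SAP 10.6 does not match the protocol's inclusive window of 24 hours to 7 days, and could flag compliant pairs or none at all

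*SAP*

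**What the plan says.** The spacing rule for the two parts of the on-study challenge is the same in all four of these places:

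- Protocol 6.1: "at least 24 hours, but not more than 7 days, apart, and not within 24 hours of a dose of study drug".
- Protocol 9.2.2.1: "at least 24 hours, but not more than 7 days apart, and not within 24 hours of a dose of study drug".
- SAP 4.5.1: "at least 24 hours, but not more than 7 days apart, and not within 24 hours of a dose of" study drug.
- SAP 10.2, footnote 5 to Table 3: "at least 24 hours, but not more than 7 days, apart and not within 24 hours of a dose of SC study drug".

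Both limits are inclusive. SAP 10.6 words the matching deviation differently. The row begins "Food challenges were not performed either on different day, more" and continues "than 1 day apart or less than 7-days apart during DBPCFC at on"-study visits V16, V22 or V25.

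The row feeds an analysis set. SAP 3.2 states: "PPS includes all subjects in the mFAS except for those who are excluded because of important protocol violations". It adds a filter: "An important protocol violation is one that may affect the interpretation of study efficacy results". It refers to 10.6 for the preliminary list, and plans PPS analyses of the primary and first secondary endpoints. SAP 5.6.1 calls the PPS analysis of the primary endpoint supportive.

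**The concern.** A deviation row should identify subjects who broke the protocol rule and no others. This row moves both limits inward: a minimum that included 24 hours becomes more than 1 day, and a maximum that included 7 days becomes less than 7 days. It also places three conditions under a single negation joined by either and or, so its logical meaning is unclear.

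Two things are at stake. First, the PPS is a check on the visit 16 results among subjects who followed the protocol; removing subjects whose challenge was correctly spaced weakens that purpose. Second, SAP 5.4 requires a summary table and a listing of protocol deviations. If these are programmed from the 10.6 wording, compliant pairs at V16, V22 or V25 could be reported as deviations, or true spacing violations could go unreported.

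**Working it through.** The plan states no figure to reproduce here. The check is a comparison of rules over the possible gaps g between the two challenge days.

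**Rules**

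- Protocol window (Protocol 6.1 and 9.2.2.1; SAP 4.5.1; SAP Table 3 footnote 5): compliant if 24 h ≤ g ≤ 7 days. In whole calendar days, 1 ≤ g ≤ 7.
- SAP 10.6, reading A (all three conditions required): acceptable only if the days differ, g > 1 day and g < 7 days. In whole days, 2 ≤ g ≤ 6.
- SAP 10.6, reading B (literal): flagged only if none of the three conditions is met, that is, same day and g ≤ 1 and g ≥ 7. No gap can be both ≤ 1 and ≥ 7, so nothing is ever flagged.

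**Counting in calendar days**

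| Gap (days) | Protocol | 10.6, reading A | 10.6, reading B |
|---|---|---|---|
| 0 | outside | flagged | not flagged |
| 1 | inside | **flagged** | not flagged |
| 2 to 6 | inside | not flagged | not flagged |
| 7 | inside | **flagged** | not flagged |
| 8 or more | outside | flagged | not flagged |

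Reading A disagrees with the protocol at gaps of 1 and 7 days. Reading B misses every true violation: same-day pairs and pairs 8 or more days apart.

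**Counting in clock time** (7 × 24 = 168 h)

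| Gap (h) | Protocol, 24 ≤ g ≤ 168 | 10.6, reading A, 24 < g < 168 |
|---|---|---|
| 23.9 | outside | flagged |
| 24.0 | inside | **flagged** |
| 24.1, 25 | inside | not flagged |
| 167 | inside | not flagged |
| 168.0 | inside | **flagged** |
| 168.1 | outside | flagged |

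By clock time, reading A disagrees only at exactly 24.0 h and exactly 168.0 h, so the practical conflict depends on counting in dates.

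**Which count is likely?** The SAP does not say. The 10.6 row drops the hours and speaks only of days. Elsewhere the SAP relies on dates: the period boundaries in 3.3 use the date of the second challenge day, 6.1 sets baseline by date alone except for AE, laboratory, PK and ADA data, and 6.4 maps unscheduled and early-termination visits by study day. A date-based check is therefore plausible, but not established.

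**After correction.** If the row flags pairs not on different days, under 24 hours apart or over 7 days apart, the accepted whole-day gaps become 1 to 7 in both places and no gap is discordant.

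**The case against.** The strongest reply is that no subject is excluded by this row as it stands. SAP 10.6 marks its list as preliminary, to be finalised before lock. SAP 3.2 limits important violations to those that could affect how efficacy is interpreted, and leaves final PPS membership to a blinded decision. The row sits in a column for protocol deviations, and a pair inside the protocol window is not one; a careful data reviewer who knew SAP 4.5.1 would pass it. By clock time a next-day pair at 25 h satisfies both rules. The PPS is supportive, and SAP 10.1 lists only the mFAS and FAS for the two endpoints concerned.

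Most of this stands, and it limits the point. A reader might infer that compliant next-day and one-week pairs are excluded; the documents support only that they could be. A reader might also try to size the loss by spreading gaps evenly over 1 to 7 days, giving 2/7 = 29%, or about 35 of the 122 planned subjects. The documents give no gap distribution to support that, and the 122 in Protocol 11.2 and SAP 2.3 includes subjects who discontinue before week 28 and so have no visit 16 pair.

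The reply does not rescue the row itself. On reading A it conflicts with the protocol, and on reading B it detects nothing. Nothing in the SAP tells the person applying 10.6 to substitute the window in 4.5.1. That the list is still preliminary is a reason to correct it now.

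**Conclusion.** The SAP 10.6 spacing row misstates the protocol window on either reading and should be reconciled with it. If gaps are computed from dates and all conditions are required, pairs 1 day or 7 days apart are compliant but could be flagged, and those subjects could be removed from the supportive PPS analyses of the primary and first secondary endpoints. If the row is read literally, it flags no pair, whatever the spacing.

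The consequence is small. The mFAS analysis of the primary endpoint and the hierarchical test do not depend on this row. Both PPS endpoints are at visit 16, so the V22 and V25 parts matter mainly for deviation reporting. The number of subjects affected cannot be computed from the documents. A claim that the PPS as a whole no longer reflects adherence would go too far: this is one row in a long list, subject to later blinded review.

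**What to change.** Before the deviation list is finalised, replace the SAP 10.6 row with the negation of the protocol rule:

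*Peanut and placebo challenges not on different days, less than 24 hours apart, or more than 7 days apart, at V16, V22 or V25.*

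Keep all three visits, because the present row covers them and footnote 5 to SAP Table 3 applies the rule to the challenges in that table.

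Also state whether the gap is derived from dates or from date/times. Dates alone cannot fully apply the 24-hour limit: a consecutive-date pair 22 h apart breaches the protocol but shows a gap of 1 day. If only dates are available, the SAP should say that a gap of 1 to 7 calendar days is taken as compliant.

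The cost is about one line of SAP text plus a derivation note. It needs no new data and leaves the primary analysis unchanged.
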